## Return to SR

The intermediate primary outcome, whether patient returns to SR at 12 months, will be summarized according to the group to which they were randomised. The comparison between the heart rhythm (AF or SR) at the baseline and 12 months will be also summarized.

For the primary endpoint analysis, the rate in SR for Routine treatment group will be compared to that for Routine+Maze treatment group using a binary logistic regression model, which will include surgeon (as a random effect), surgical procedure and baseline heart rhythm as fixed effects. The odds ratio for the rate of return to SR at 12 months of Routine treatment group against Routine+Maze treatment group will be reported with 95% confidence interval and p-value for the data seen, under the null hypothesis that the rates of return to SR at 12 months are no different between the pairs of groups.

The adequacy of the logistic regression models for the primary endpoint will be assessed by examining the following statistics and relevant graphical summaries:

Pearson Residuals/Deviance (Half-normal plots)

Leverage values.

Cook's Distance.

Cross validation probabilities (the probability of a particular observation, conditional on the remaining observations).

L-statistics (the influence of an observation on the difference in deviance due to fitting an the treatment effect).

Actual percentage time in AF across the 4 days of monitoring at baseline and at 12 months, i.e. the percentage of time that the patient is in AF if their predominant rhythm is SR, is reported by treatment group. Based on the interim report, the percentage time

in AF is almost dichotomized at 0% and 100%. Therefore, only summary statistics are reported in this case.

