## 1.2 Study design

The Amaze trial is a pragmatic, multicentre, prospective, double blind, randomised controlled trial to compare clinical, patient-based and cost outcomes for patients with pre-existing AF who undergo routine cardiac surgery either with or without an adjunct device-based ablation procedure.

The trial is double blind to the extent that neither the patient nor the cardiologist who analyses the 4 day ECG, nor the quality of life assessor should be aware which group the patient has been allocated to.

Eligible patients are randomised (in a 1:1 ratio) to receive either their routine cardiac surgery with no additional procedure or their routine cardiac surgery with an additional device-based AF ablation procedure.

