#### Return to SR at 12 months

Published RCTs of ablation as an addition to cardiac surgery have reported rates of return to SR at 12 months [7][8][9][10][11] ranging from 44% to 87% in the trial arms and 5% to 33% in the control arms. If we take a conservative estimate of the difference between the groups (45% vs. 30%) then we would have 80% power to detect this difference with a sample size of 176 in each group, total 352 (2-sided significance 5%). With recruitment of 400 patients this would allow for deaths or loss to follow up at 12 months of approximately 15%.

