### 4.2 Baseline data collection

We adhere to the ACC/AHA/ECS 2006 Guidelines which recommend that the initial patient description includes demographics, type and duration of AF and the planned cardiac procedure.

The first 4-day ECG recording starts after the patient attends the preadmission clinic and has consented to participate. All other baseline measurements are recorded on the day of admission for surgery. Once these measurements have been taken, the patient is registered with the co-ordinating centre's R&D unit and randomised as described in Section 1.5.

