#### 5.5 Subgroup Analysis

Subgroup analysis will include those patients for whom measurements are available.

The first objective of subgroup analysis is within the whole dataset, to account for potential variation in the treatment effects between

patients with paroxysmal and non-paroxysmal AF: Paroxysmal AF vs. Persistent Chronic or longstanding AF.

individual centres (as a random effect to allow for heterogeneities in small centres

different cardiac surgical procedures

different surgeons.

different lesion sets.

The different lesion sets are to be defined as follows:

minimal LA lesion set: pulmonary vein isolation only ± LA appendage line

more extensive LA lesion set excluding mitral annulus

more extensive LA only lesion set including mitral annulus

minimal LA lesion set + RA lesion set

more extensive LA lesion set excluding mitral annulus + RA lesion set

more extensive LA lesion set including mitral annulus + RA lesion set

In the event that patients are too sparsely-distributed across the 6 categories, the categories will be combined into 4, by combining (i) with (ii) and combining (iv) with (v). If this is still too sparse to facilitate comparison, then the lesion set subgroup will be reduced to a comparison of category (vi) to all other groups.

For the Quality-Adjusted Survival Endpoint, a linear regression model will be fitted to the Area Under the Utility Curve, with baseline EQ5D score, surgeon, surgical procedure, treatment group, subgroup variable and the subgroup-by-treatment interaction variable. The treatment modifying effect will be reported with a 95% confidence interval. The Area under the utility curve will be appropriately transformed prior to performing subgroup analyses, and the results back-transformed where necessary.

For the Return to SR Endpoint, a logistic regression model will be fitted to heart rhythm at 12 months with the baseline heart rhythm, surgeon, surgical procedure, treatment group, subgroup variable of interest and its interaction term with treatment group. The odds ratio of the interaction term between treatment and subgroup variable will be reported with 95% confidence interval and p-value for the data seen, under the null hypothesis that there is no difference in the treatment effects on patients within different subgroup of interest.

The second objective is within the Routine+Maze treatment group, to account for variation in the treatment effects between

different ablation devices

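### The 12-month SR model omits AF type, a baseline variable that could be pre-specified for a small to modest gain in efficiency

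*SAP*

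**What the plan says.** - **Primary model.** Section 5.4 (Return to SR) compares the groups by logistic regression with "surgeon (as a random effect), surgical procedure and baseline heart rhythm as fixed effects". The same section describes baseline rhythm as AF or SR.
- **Baseline data.** Section 4.2 says the trial follows guidelines under which "the initial patient description includes demographics, type and duration of AF and the planned cardiac procedure". It places the baseline measurements before randomisation. Section 1.6 makes documented chronic, persistent or paroxysmal AF an inclusion criterion.
- **Where AF type is used.** Section 5.5 has a subgroup analysis of "patients with paroxysmal and non-paroxysmal AF: Paroxysmal AF vs. Persistent Chronic or longstanding AF". No model in the SAP contains AF duration.
- **Imputation.** Section 2.3 imputes missing 12-month rhythm from baseline rhythm, surgeon, procedure and treatment group.
- **Reason for the short list.** Section 2.3 notes that the covariates chosen are recorded at once, so few missing values are expected.
- **No later additions.** Section 5.2 rules out model building; only variables named in advance enter.
- **Sample size.** Section 1.4.1 claims "80% power to detect this difference with a sample size of 176 in each group" for 45% versus 30%. It mentions no covariate adjustment.

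**The concern.** Baseline rhythm is a coarse stand-in for how established the AF is. Section 1.6 defines persistent AF as lasting beyond 4 days and longstanding AF as persistent beyond 1 year, so patients of both kinds would be expected to show AF throughout a 4-day recording. Section 5.4 adds that percentage time in AF clusters near 0% and 100%, so the recording offers little gradation.

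Randomisation is stratified by surgeon and planned procedure (Section 1.5), so the design does not balance AF type. If type carries prognostic information beyond baseline rhythm, the primary analysis forgoes some power and leaves chance imbalance in type unadjusted. The imputation model has the same gap. With 400 recruited and 352 needed for analysis, 400 − 352 = 48 outcomes could be missing, and imputation would be less credible if loss were related to AF type. Because Section 5.2 admits only named variables, the term has to be specified now or not at all.

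**Working it through.** **1. The plan's own figure.** Inputs from Section 1.4.1: 45% versus 30%, two-sided 5%, 80% power. Allocation is 1:1 (Section 1.2). The pooled rate is (0.45 + 0.30)/2 = 0.375.

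Without continuity correction:

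n = [1.96·√(2·0.375·0.625) + 0.8416·√(0.45·0.55 + 0.30·0.70)]² / 0.15² = (1.342 + 0.569)² / 0.0225 ≈ 162.3, so 163 per group.

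With continuity correction:

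n′ = (n/4)·[1 + √(1 + 4/(n·0.15))]² = (162.3/4)·(1 + 1.079)² ≈ 175.4, so 176 per group.

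The SAP's 176 is reproduced exactly. At 176 per group, the unadjusted test without correction has

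power = Φ[(0.15·√176 − 1.342)/0.676] = Φ(0.958) = 83.1%.

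The planned 80% is therefore met with no covariate at all.

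**2. What the extra terms could add.** The SAP gives no prognostic strength for AF type or duration, so this step rests on assumptions. A simulation of 4,000 trials per scenario used 352 patients, with marginal rates held at 30% and 45%. Assumed covariates:

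- 25% of patients paroxysmal
- baseline SR in 75% of paroxysmal patients and 12% of the others
- standardised log duration, 0.4 SD shorter in paroxysmal patients

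Type entered as paroxysmal or not. Surgeon and procedure were left out. The test was the Wald test for treatment.

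The information gain is [(z after + 1.96)/(z before + 1.96)]² − 1, where z is the normal quantile of the power.

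| Assumed OR for SR: baseline rhythm; type; duration per SD | Power with baseline rhythm | Plus type and duration | Gain (points) | Information gain |
|---|---|---|---|---|
| 4; 1; 1 (no added value) | 85.5% | 85.6% | 0.2 | about 0% |
| 4; 1.5; 0.8 | 88.0% | 88.5% | 0.6 | 2% |
| 4; 2; 0.67 | 88.9% | 90.1% | 1.2 | 4% |
| 4; 3; 0.5 | 88.6% | 91.9% | 3.4 | 13% |
| 4; 4; 0.4 | 88.9% | 93.8% | 4.9 | 21% |
| 8; 1; 1 (no added value) | 89.8% | 89.8% | 0.0 | 0% |
| 8; 2; 0.67 | 91.9% | 92.8% | 0.9 | 4% |
| 8; 3; 0.5 | 92.6% | 94.7% | 2.1 | 10% |

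Gains are taken from unrounded powers. For example, row 4 gives [(1.400 + 1.96)/(1.204 + 1.96)]² = 1.13.

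**3. Reading the table.** Baseline rhythm, already in the model, contributed about 3 to 9 points over no adjustment. Type and duration together added 0 to 5 more. With no added prognostic value, nothing material was lost. The share due to AF type alone was not separated.

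**4. Scale of the odds ratio.** For the same 45% versus 30%, the treatment odds ratio conditional on all the simulated covariates ran from about 2.0 to 2.7. The unadjusted value is (0.45/0.55)/(0.30/0.70) = 1.91.

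**The case against.** The strongest reply is that nothing here is wrong. The model contains both stratification factors and the baseline value of the outcome, its covariates are fixed in advance, and its test is valid without further terms. That stands, and it limits this point to a suggestion about efficiency.

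The plan also has a reason for its short list: the chosen variables are recorded at once. A reader might infer that the omission buys nothing, but Section 2.3 does not support that. The reason is weak for AF type, which is tied to the entry criterion, and more plausible for duration. Section 4.2 does not show that duration is held in years or how completely. Its meaning for paroxysmal patients is unclear, and it overlaps with the persistent/longstanding split.

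Section 5.5 does fit AF type beside the primary covariates. However, that model includes an interaction and is limited to patients with measurements available, so it does not supply the primary estimate.

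A reader might also infer that the omission biases the treatment effect towards zero. The change in the log odds ratio when a prognostic covariate is left out is non-collapsibility: the two models estimate differently conditioned odds ratios. Chance imbalance is already allowed for in the error rate of a randomised comparison; adjustment improves precision.

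**Conclusion.** The omission is real and worth repairing, as an efficiency improvement. If AF type predicts SR beyond baseline rhythm, the gain is small to modest: about 0 to 5 points of power at the planned rates for type and duration together. The assumed prognostic odds ratios and covariate frequencies drive this range, and the SAP can neither confirm nor narrow it.

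A reader might infer a definite or larger loss of power. A gain of about 7 points (59.8% to 66.7%) does appear under strong prognostic assumptions if the rates are set near 31% versus 43%. That is not the plan's contrast. Unadjusted power there is only about 65% at 176 per group, where the power curve is steeper. At 45% versus 30% the largest gain found was 4.9 points, and the stated 80% is met without any of these terms.

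**What to change.** Before unblinding, name AF type (paroxysmal, persistent, longstanding) as a fixed effect in three places:

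- the 12-month SR model (Section 5.4)
- the 24-month SR model (Section 5.6)
- the imputation model for 12-month rhythm (Section 2.3)

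Add AF duration only if a blinded check shows that it is completely recorded and the SAP defines it, including for paroxysmal patients.

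The cost is a line of text in each section and two parameters for AF type. The reported odds ratio becomes conditional on one more covariate, which the SAP should state. Section 2.3 already provides for imputing any missing covariate values. The sample size does not change.

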#### 5.4.1 Sensitivity Analysis

For the final primary endpoint (Quality-adjusted Survival), we will impute as zero any EQ5D utility value that is missing due to the patient death. Any remaining missing values will be imputed using multiple imputation. For the sensitivity analysis, a Last Observation Carried Forward approach will be used to impute missing (nonzero) utility values at 24 months, and any missing intermediate utility values. Alternative imputation techniques will be considered. We will additionally consider a sensitivity analysis using SF6D-derived utility values and other valuation methods as appropriate.

If missing, the intermediate primary endpoint (heart rhythm) will be estimated by multiple imputation technique. If more than 5% of patients are withdrawn or lost to follow-up before the 12 months is reported, then the following methods will be used as sensitivity analyses to estimate the primary endpoint:

1. a 'death=AF, censored=AF' strategy: If a patient is withdrawn or lost to follow-up within the 12 months, he will be assumed to be in AF.

2. a 'death=AF, censored=OMIT' strategy: If a patient dies for any cause within 12 months, he will be assumed to be in AF at 12 months. If a patient is withdrawn or lost to follow-up but is alive within 12 months, his record will not be included into the sensitivity analysis.

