### 2.3 Missing data

Data management will focus on the consenting process, participant eligibility, safety, data consistency and test outcomes. Attempts will be made to retrieve missing data on these areas via a thorough data cleaning process.

The levels of missing data and reasons for missingness will be investigated for the consenting process, participant eligibility, safety, data consistency and test outcomes. The quantity of missing data will be monitored by treatment group, and a summary of the number of patients with missing primary endpoint data and the quantity of missing data by treatment group will be reported.

For the intermediate primary endpoint (return to sinus rhythm at 12 months), if a patient withdraws consent or is lost to follow-up for further participation within 12 months, multiple imputation used to impute missing outcome (AF or SR at 12 months) as a function of the baseline heart rhythm, surgeon, surgical procedure and treatment group. Rubin's rules will be used to combine imputed datasets. If more than 5% of patients are withdrawn or lost to follow-up before 12 months, then the outcome will be imputed under the alternative patterns as sensitivity analyses. (See section 5.4.1)

For the final primary endpoint (Quality-Adjusted Survival at 2 years), where a patient is deceased before the end of follow-up, the utility value of 0 will be imputed for all

subsequent assessments. If the response is missing, and the patient is not known to be deceased, the missing value will be imputed using the method of multiple imputation. A “Last Observation Carried Forward” approach will be used as an alternative imputation technique for imputing other (non-death) missing values in a sensitivity analysis.

The primary analysis model will only require the baseline rhythm, surgeon and surgical procedure which are immediately recorded when patients attend the preadmission clinic and has consented to participate or during the period of surgery, so there is little concerns about missing data arising in this model. If any missing values in the covariates are reported, they will be imputed using a function of the known covariates and primary outcomes of interest.

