### 5.4 Analysis of Primary Endpoints

#### Quality-Adjusted Survival

For the final primary outcome, QALYs will be estimated from serial measurements of the EQ-5D for each patient up to 2 years using interpolation. The Health Economics analysis will be given in Section 6.

At baseline, on discharge and at 6 weeks, 6 months, 12 months and 24 months post-surgery all patients complete the EuroQol questionnaire, including the EQ-5D. The social tariff for the EQ-5D, as estimated by Dolan et al. [17] will be applied to each patient's self-reported classification in order to calculate utility values. Using actual rather than nominal times of assessment, and assuming a linear change in values between time points, patient-specific utility curves up to 24-months post randomisation will be calculated. A value of zero will be applied at the date of death for those patients who died.

The QALYs experienced by each patient to 24-months post randomization are calculated as the area under their utility curve to 24 months or time of death, whichever occurs first, where the true test dates rather than nominal test dates will be utilized in plotting the utility curve. In order to adjust for differences in baseline utilities a linear regression will be fitted to the utilities post treatment, with baseline utility and treatment group as explanatory variables. The linear regression will also include a random effect for surgeon if it is feasible to fit, and yields a positive variance component for the surgeon effect. Adjusted treatment effects will be taken from the treatment group coefficient of this regression. For patients who do not complete all EuroQoL measurements and are censored the methods of Willan and Lin[18] will be used to estimate mean QALYs and costs. The adequacy of model fit for the linear regression model at each timepoint will be assessed by examining distributions of standardised residuals, association with the predicted values, as well as identifying influential observations by referring to leverage statistics.

The differences in Quality-adjusted Survival will be presented. A confidence interval for the true difference will be formed using a non-parametric bootstrap resampling approach: [19]

A simple random sample with replacement will be drawn from the full analysis dataset of the same size as the full dataset. (ie some patients may be drawn more than once)

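### The only sensitivity analysis fixed for missing EQ-5D is last observation carried forward, a weak and ungraded check on the multiple imputation behind the QALY endpoint

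*SAP*

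**What the plan says.** The final primary endpoint is the QALY total over two years, the area under each patient's EQ-5D utility curve. The schedule is in SAP section 5.4 (Quality-Adjusted Survival): "At baseline, on discharge and at 6 weeks, 6 months, 12 months and 24 months post-surgery all patients complete the EuroQol questionnaire". The curve joins the available points by straight lines: "assuming a linear change in values between time points, patient-specific utility curves up to 24-months post randomisation will be calculated".

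Utilities after death are set to zero. For the rest, section 5.4.1 says: "Any remaining missing values will be imputed using multiple imputation". The sensitivity analysis follows: "a Last Observation Carried Forward approach will be used to impute missing (nonzero) utility values at 24 months, and any missing intermediate utility values". Section 2.3 gives last observation carried forward (LOCF) the same role; it "will be used as an alternative imputation technique for imputing other (non-death) missing values in a sensitivity analysis".

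Two further sentences in 5.4.1 leave options open. "Alternative imputation techniques will be considered" names no method. "We will additionally consider a sensitivity analysis using SF6D-derived utility values and other valuation methods as appropriate" concerns how health states are valued, not what is assumed about missing forms.

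For heart rhythm, by contrast, 5.4.1 sets out two explicit scenarios, to be run if more than 5% of patients are withdrawn or lost before 12 months.

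**The concern.** Multiple imputation in its usual form assumes that data are missing at random, and the SAP says nothing to the contrary. A sensitivity analysis should show how far that assumption can fail before the conclusion changes. LOCF does this poorly here, for three reasons.

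- **Early values are held for a long time.** Two of the five post-baseline visits fall within six weeks of cardiac surgery, when utility can be expected to be temporarily low. That is a clinical expectation; the SAP gives no utilities. A living patient with no form after either visit is assumed not to recover for the rest of the two years.
- **Later information is not used in filling gaps.** A missing 6-month value takes the 6-week value even when the 12-month value is known. The 12-month value stays in the curve but does not inform the filled point.
- **Filled values are treated as known.** The bootstrap in 5.4 resamples patients. Applied to data already completed by LOCF, it does not reflect doubt about what the missing values were.

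At stake is how a reader interprets agreement or disagreement between the two analyses. The departure from the primary assumption is set by when forms stop and by the recovery path. It is not set by a stated scenario, and it cannot be graded or applied to one arm.

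**Working it through.** **The plan's own figure.** Section 1.4.1 gives SD 0.3, 200 per group, target 0.083 QALY and two-sided 5%. The standard error of the difference is 0.3 × √(2/200) = 0.03. Power is Φ(0.083/0.03 − 1.96) = Φ(0.807) = 0.79, which agrees with the stated figure of about 80%. It does not depend on LOCF; 0.083 and 0.03 serve below as yardsticks.

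**Assumed inputs.** The SAP gives neither utilities nor the timing of drop-out. Path A is an illustration: days 0, 8, 42, 183, 365 and 730, with utilities 0.70, 0.60 (or 0.50), 0.70, 0.77, 0.78 and 0.77. Discharge on day 8 is also assumed.

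**Formula.** QALY = Σ (interval in days) × (mean of the two end utilities) / 365.

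**Full curve, discharge 0.60.** (8×0.65 + 34×0.65 + 141×0.735 + 182×0.775 + 365×0.775)/365 = 554.86/365 = 1.520. With discharge 0.50 it is 552.76/365 = 1.514.

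**LOCF when no later form exists**

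| Last form | LOCF area | Change for that patient |
|---|---|---|
| Discharge, 0.60 | (5.2 + 722×0.60)/365 = 1.201 | −0.319 |
| Discharge, 0.50 | (4.8 + 722×0.50)/365 = 1.002 | −0.512 |
| 6 weeks, 0.70 (discharge 0.60) | (27.3 + 688×0.70)/365 = 1.394 | −0.126 |
| 6 months, 0.77 | 1.513 | −0.007 |
| 12 months, 0.78 | 1.525 | +0.005 |

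**Second assumed path.** Baseline 0.70, discharge 0.55 on day 10, a 6-week value 0.05 to 0.20 below a plateau of 0.80 from 6 months. The changes are −0.44 to −0.47 after discharge, −0.085 to −0.34 after 6 weeks, and 0 after 6 or 12 months.

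**Single gap at 6 months, 12 months observed (path A).** LOCF puts in 0.70 for 0.77: −0.07 × (141+182)/2/365 = −0.031. A straight line gives 0.70 + 0.08×141/323 = 0.735, so the error is −0.016. Both err downwards, and LOCF errs by 0.015 more.

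**From patient to treatment difference.** The shift in the difference is the excess proportion lost in one arm times the per-patient change.

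- Equal loss and equally low held values: no shift from the early dip.
- A 3- to 5-point excess (6 to 10 of 200) lost after discharge: 0.03×0.319 = 0.010 to 0.05×0.512 = 0.026, or 12% to 31% of 0.083.
- The same excess after 6 weeks: 0.03×0.126 = 0.004 to 0.05×0.126 = 0.006, or 5% to 8% of 0.083.
- A 10-point excess (10% against 20%) with a per-patient change of 0.10 to 0.40: 0.010 to 0.040.

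**Dilution under equal loss.** If the whole benefit arises after the last form, a lost share d contributes none of it and the difference becomes 0.083×(1−d). For d of 5%, 10% and 15% this is 0.079, 0.075 and 0.071. The 15% matches the SAP's allowance for deaths and loss together by 12 months, so it is generous for living patients lost this early.

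**The case against.** LOCF is only a sensitivity analysis; the primary result rests on multiple imputation. Section 5.4 also names inverse weighting for censored patients, and 5.4.1 leaves room for other techniques. The large figures are per affected patient, under assumed utilities, and should not be read against a between-group target. With a 3- to 5-point imbalance the shift stays below one planning standard error, and nothing in the SAP predicts such an imbalance; patients are blinded to allocation. All of this stands, and it makes the point a minor one. It does not supply the missing check: the weighting belongs to the main analysis text, and the other techniques are unnamed.

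A reader might infer more than the SAP supports:

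- **That LOCF overrides later observed values.** It fills only missing ones, and later observations remain in the curve.
- **That it contradicts the linear-change rule in 5.4.** That rule builds the area once values are in place; the rule for missing values is multiple imputation. A sensitivity method may differ from the main one.
- **That it biases the trial's result.** It cannot alter the primary estimate, and its effect on the arm difference in the sensitivity analysis is conditional.
- **That it says nothing about data missing not at random.** It imposes a crude no-recovery assumption, and stability under it is weak evidence, but not none.

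**Conclusion.** The point holds as a modest improvement to the plan. LOCF is the only missing-data sensitivity analysis that the SAP fixes for EQ-5D, and it is a poor test of the multiple imputation for the reasons given above.

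Its effect on the treatment difference cannot be fixed from the SAP. It depends on the timing and balance of drop-out and on the recovery path, none of which is given. Under the utilities assumed here, the shift is 0.004 to 0.026 QALY for a 3- to 5-point imbalance. It reaches 0.040, above the planning standard error, only with a 10-point imbalance and a large per-patient change. With balanced loss, only dilution of a later benefit remains.

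**What to change.** In sections 2.3 and 5.4.1, make the pre-specified sensitivity analysis a delta-adjusted multiple imputation:

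- Use the same imputation model as the primary analysis.
- Shift the imputed utilities of living patients by a range agreed before database lock, for example 0.05, 0.10 and 0.15 lower. These values are proposals, not taken from the SAP.
- Apply the shifts in Routine+Maze alone, in Routine alone, and in both arms.
- Obtain the interval in the same way as for the primary multiple-imputation analysis, consistent with the bootstrap in 5.4.
- Report the shift at which the conclusion changes.

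LOCF may stay as a supplementary analysis. The cost is SAP wording, a few more runs of an imputation already planned, and agreement on the shift values. No extra data are needed.

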## 3 Population

### 3.1 Intention-to-treat Analysis

An intention-to-treat analysis will be the primary method for analysing and summarising the trial data. The intention-to-treat population is defined as all randomised patients, regardless of eligibility, withdrawal, compliance with the protocol, loss to follow-up or actual treatment received. Only patients who have withdrawn their consent for their data to be used in the study, or for whom written informed consent has not been received, will be excluded in this population. These patients will be analysed and summarised according to the intervention they were randomised to receive.

If more than 5% tests or trial conduct constitute a major protocol violation such as cross-over to the other arm or cancelling surgeries, the Complier Average Casual Effect analysis will be considered.

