## 5.6 Key Secondary Endpoint Analysis

The key secondary endpoint, the rate to return stable SR at 24 months will be analysed in a similar way to the rate of return to SR at 12 month, but will include only those patients for whose measurements are available. The rate in SR at 24 months for Routine treatment group will be compared to that for Routine+Maze treatment group using a binary logistic regression model including baseline heart rhythm, surgeon, surgical procedure and treatment group. The odds ratio for the rate of return to SR at 24 months of Routine treatment group relative to the Routine+Maze group will be reported with 95% confidence interval and p-value for the data seen, under the null hypothesis that the rates of return to SR at 24 months are no different between the pairs of groups.

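### The plan has no consistent rule for deaths in the return-to-SR analyses at 12 and 24 months, and its death=AF checks depend on a 5% withdrawal trigger

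*SAP*

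**What the plan says.** Return to SR at 12 months is the intermediate primary endpoint. Five statements in the SAP bear on patients who die first.

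- Section 2.3 (Missing data): "if a patient withdraws consent or is lost to follow-up for further participation within 12 months, multiple imputation used to impute missing outcome". The imputation model predicts rhythm "as a function of the baseline heart rhythm, surgeon, surgical procedure and treatment group". Death is not mentioned for this endpoint. For the QALY endpoint the same section does treat death separately, setting utility to 0 afterwards.
- Section 5.4.1 (Sensitivity Analysis): "If missing, the intermediate primary endpoint (heart rhythm) will be estimated by multiple imputation technique". No cause of missingness is excepted.
- Section 3.1 (Intention-to-treat Analysis): "The intention-to-treat population is defined as all randomised patients, regardless of eligibility, withdrawal, compliance with the protocol, loss to follow-up or actual treatment received". The only exclusions are patients who withdrew consent to use of their data or gave no written consent.
- Section 5.4.1 adds two sensitivity strategies, started by this condition: "If more than 5% of patients are withdrawn or lost to follow-up before the 12 months is reported". The first reads "a 'death=AF, censored=AF' strategy: If a patient is withdrawn or lost to follow-up within the 12 months, he will be assumed to be in AF". The second says of deaths: "If a patient dies for any cause within 12 months, he will be assumed to be in AF at 12 months". It omits patients who are withdrawn or lost but alive.
- Section 5.6 (Key Secondary Endpoint Analysis) models SR at 24 months in a similar way, "but will include only those patients for whose measurements are available".

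**The concern.** A patient who dies before 12 months has no 12-month rhythm, and the plan does not say once and clearly what value that patient contributes. Section 5.4.1 read with Section 3.1 leads to an imputed SR or AF, as if the patient were alive. Section 2.3 leaves the case open. The choice decides what the primary comparison estimates: rhythm in a hypothetical population without deaths, rhythm among survivors, or being alive and in SR. Left open, it could be settled after the data are seen.

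The omission looks unintended. The plan handles death explicitly for QALYs, and it labels both SR sensitivity strategies death=AF. But those strategies are conditional on withdrawal and loss, which is the wrong gate for a question about deaths. The text of the first strategy does not define what happens to deaths, although its label does.

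At 24 months the same endpoint follows a different rule. Deaths and all other missing patients drop out, and the 12-month rhythm, an obvious predictor of the missing value, is not used.

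**Working it through.** **Inputs.** From SAP Section 1.4.1: SR at 12 months 45% (maze) vs 30% (routine), 80% power, two-sided 5%, 176 per group, 400 recruited, about 15% deaths or loss combined. Allocation is 1:1 (Section 1.2). The SAP gives no mortality rate, so every mortality figure below is an assumption, shown as a range. The 45% and 30% are taken as the SR rates in survivors.

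**The plan's own figure.** With mean proportion 0.375 and difference 0.15:

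n = [1.960·√(2·0.375·0.625) + 0.842·√(0.45·0.55 + 0.30·0.70)]² / 0.15² = 163 per group after rounding up.

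The continuity-corrected version gives 176, an exact match. No stated figure is in dispute.

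**The trigger.** 5% of 400 is 20, so the strategies start at 21 or more patients withdrawn or lost. Suppose 4% (16) are withdrawn and 8% (32) have died. If deaths do not count, the trigger is not met and no analysis scores death as AF. If deaths count, 48 exceeds 20 and the strategies run.

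**Effect of the death rule at 12 months.** Let s be the SR rate in survivors and d the mortality in an arm.

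- Death imputed from treatment group and the analysis covariates: expected rate (1−d)·s + d·s = s. The difference stays at 45 − 30 = 15.0 points (odds ratio 1.91) whatever d is.
- Deaths left out: the rate is again s, so the difference is also 15.0 points, in fewer patients.
- Death counted as not in SR: expected rate (1−d)·s.

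Results for the last rule, with 200 per arm and no other attrition. Power is without continuity correction. Odds ratios are maze relative to routine.

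| Mortality, maze / routine | SR, maze / routine | Difference (points) | Odds ratio | Power |
|---|---|---|---|---|
| 0% / 0% | 45.0% / 30.0% | 15.0 | 1.91 | 87.5% |
| 2% / 2% | 44.1% / 29.4% | 14.7 | 1.89 | 86.5% |
| 5% / 5% | 42.75% / 28.5% | 14.25 | 1.87 | 84.8% |
| 8% / 8% | 41.4% / 27.6% | 13.8 | 1.85 | 83.0% |
| 10% / 10% | 40.5% / 27.0% | 13.5 | 1.84 | 81.7% |
| 5% / 3% | 42.75% / 29.1% | 13.65 | 1.82 | 81.4% |
| 8% / 4% | 41.4% / 28.8% | 12.6 | 1.75 | 75.4% |
| 10% / 5% | 40.5% / 28.5% | 12.0 | 1.71 | 71.5% |
| 4% / 8% | 43.2% / 27.6% | 15.6 | 2.00 | 90.7% |

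**What imputation does with the deaths.** At 8% / 4% there are 16 and 8 deaths. Imputation would on average put 16·0.45 = 7.2 and 8·0.30 = 2.4 of them in SR, and the remaining 8.8 and 5.6 in AF.

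**24 months.** Assume 85% agreement between 12- and 24-month rhythm. True SR is then 0.45·0.85 + 0.55·0.15 = 0.465 and 0.30·0.85 + 0.70·0.15 = 0.360, a difference of 10.5 points. Now assume dropout of 12% after AF and 4% after SR.

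- Maze available cases: (0.45·0.96·0.85 + 0.55·0.88·0.15) / (0.45·0.96 + 0.55·0.88) = 0.4398/0.916 = 0.480.
- Routine available cases, same pattern: 0.3372/0.904 = 0.373. Difference 10.7 points, a bias of about 0.2.
- Routine with a flat 4% dropout instead: 0.360. Difference 12.0 points, a bias of 1.5.

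**The case against.** The strongest reply is that this is a gap in wording with small consequences. Much of that stands, and several stronger readings that a reader might draw are not supported.

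- *The SAP says that deaths will be imputed.* No sentence says so. It follows from the unrestricted rule in Section 5.4.1 and the population in Section 3.1, while Section 2.3, the fuller account of the method, names only withdrawal and loss. The supportable claim is that the sections must be reconciled.
- *Death is never a failure in the primary result.* Not so under imputation: at the assumed rates most imputed deaths would fall in AF (8.8 of 16 and 5.6 of 8 above). Death is simply not scored as failure by rule.
- *Deaths do not count towards the 5%.* This is unclear. The second strategy sets apart patients who are lost but alive, which hints that the lost may include the dead. On that reading, attrition near the planned 15% (60 of 400) would start the strategies. At or below 5% combined they would still not run.
- *A mortality difference would be hidden.* Survival is a secondary outcome (Section 2.2), deaths are tabulated (Section 5.9), and death enters the QALY endpoint as zero. Only its effect on the SR comparison is lost.
- *The planned effect would shrink by a sixth.* The 12.6-point figure needs an assumed 8% vs 4% imbalance. Section 1.1.1 describes device ablation as generally safe with little added operative burden, and the opposite imbalance raises the difference to 15.6.
- *The 24-month analysis is materially biased.* The 1.5-point figure needs rhythm-dependent dropout in the maze arm alone, which is hard to motivate when patients are blinded (Section 1.2).

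What remains is that a primary endpoint has no settled death rule, and that the check on it is conditional.

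**Conclusion.** The point holds as an inconsistency that should be fixed. Sections 2.3, 3.1 and 5.4.1 do not give one rule for death before 12 months, the primary analysis does not score death as failure, and the death=AF strategies depend on a trigger whose scope is unclear. Section 5.6 applies a different rule at 24 months and sets aside the 12-month rhythm.

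The size depends on mortality, which the SAP does not state. Low and balanced mortality matters little: at 5% in both arms the expected difference is 14.3 instead of 15.0 points. Across the assumed imbalances it runs from 12.0 to 15.6 points, and power with 200 per arm from about 71% to 91%. These figures assume the planned rates in survivors and no other attrition. They show how far the choice of rule can move a primary result, and do not predict a bias in a known direction.

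**What to change.** 1. Reconcile Sections 2.3 and 5.4.1 with one sentence: a patient who dies before the assessment is counted as not in SR, at 12 and at 24 months. This is the rule that the labels of both existing strategies already carry.
2. Restrict multiple imputation to patients known to be alive with a missing rhythm.
3. Run the death and censoring sensitivity analyses whatever the level of withdrawal or loss, write the handling of deaths into the text of the first strategy, and report an alive-only analysis as supportive.
4. In Section 5.6, replace the available-case rule with multiple imputation for patients alive at 24 months, with the 12-month rhythm as a predictor.

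The cost is a change of SAP wording and modest extra programming. The quoted SR rates will be slightly lower, because they will mean alive and in SR.
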